5.1 Method of Assigning Subjects to Treatment Groups

Subjects will be randomly assigned to 1 of 3 treatment groups, in a 1:1:1 ratio, as presented in Table 3-1, and operationally managed to maintain a minimum number of subjects enrolled in 2 age groups: 6 to 10 years, inclusive; and 11 to 17 years, inclusive. A staggered enrolment is planned: the first 45 subjects enrolled will be in the older age group of 11 to 17 years, inclusive, and designated the safety lead-in cohort. After reactogenicity for the safety lead-in cohort is reviewed by the medical monitor, medical lead, and SMC chairman (with appropriate consultation with investigators, if needed), the remainder of subjects will be enrolled. An interactive response technology (IRT) system will be used to administer the randomization schedule centrally. The IRT system will also be designed to distribute the full cohort into groups to provide mid-turbinate/nasopharyngeal samples for *B. pertussis* culture or PCR on Day 29 or 85; however, if a subject cannot provide a sample on Day 29 (for any reason), the subject should provide a sample on Day 85 (this will not be considered a protocol deviation). Biostatistics will generate the randomization schedule using SAS® software Version 9.3 or later (SAS Institute Inc, Cary, North Carolina) for the IRT, which will link sequential subject randomization numbers to treatment codes. The randomization schedule will be created by the dedicated randomization team, stored in a separate project area, and will be blinded to the project team with the exception of an unblinded team who will manage vaccine logistics, preparation, and administration, but will not be involved in

study-related assessments or have subject contact for data collection following study vaccination.

Enrolled subjects may participate in an optional substudy in which subjects may elect to participate at any time from the day of enrolment through Day 85. No randomization is planned for the substudy as all subjects participating in the open-label substudy will receive an intranasal re-vaccination/attenuated challenge with BPZE1 on Day 85. It is recognized this may introduce some subject bias due to the opt-in nature, but this has been deemed acceptable by the sponsor.

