2.2.2. Colonization (Optional Substudy Only)

- To describe colonization in each of the groups: BPZE1, BPZE1 + Boostrix, BPZE1 and BPZE1 + Boostrix, Boostrix control.

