2.3.3. Colonization (Optional Substudy Only)

- To demonstrate prior vaccination with BPZE1 substantially reduces colonization at Days 92 and Day 99

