3.2. Study Endpoints

3.2.1. Primary Endpoints

Immunogenicity

- GMFR of BPZE1 induction of mucosal S-IgA against WCE at Day 29 by treatment group (BPZE1, BPZE1 + Boostrix).

Safety

- Occurrence of solicited AEs including local, nasal/respiratory, and systemic reactogenicity events through 7 days following first study vaccination with any combination of pertussis-containing vaccines.

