$$H_0: \ln(\mu_{D29}) - \ln(\mu_{BL}) \leq 0 \text{ vs. } H_A: \ln(\mu_{D29}) - \ln(\mu_{BL}) > 0$$

After natural logarithmic transformation, a paired *t*-test will be used to test the difference of mucosal S-IgA against WCE at Day 29 compared with baseline. The superiority objective will be demonstrated if the lower limit of the 95% CI for the difference of mucosal S-IgA against WCE at Day 29 compared to baseline on the natural log scale is greater than 0. The superiority hypothesis will be tested in treatment groups BPZE1 and BPZE1 + Boostrix separately. These 2 primary comparisons will be tested at a one-sided significance level of 0.025. The study is considered a success if both primary comparisons meet statistical significance.

Sensitivity analysis for primary endpoints will be performed based on the Immunogenicity Analysis Set.

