8.4. Analyses of Endpoints for the Optional Substudy

8.4.1. Analysis of Colonization Endpoints

Colonization summary tables will be produced based on the sample type (mid-turbinate swab and nasopharyngeal swab).

The analyses in this section of the colonization substudy will be based on the PP immunogenicity analysis set but include only subjects who are enrolled in the optional open-label substudy. A sensitivity analysis will be conducted using the Immunogenicity Analysis Set but include only subjects who are enrolled in the optional open-label substudy.

To assess if prior BPZE1 induced mucosal immunity substantially reduces colonization at Days 92 and 99, the proportion of subjects with colonization at Day 92 or Day 99 will be analyzed. The 2-sided 95% CI in the proportion of subjects with colonization at either Day 92 or Day 99 (*B. pertussis* culture or PCR) will be calculated using Agresti-Coull method and summarized by treatment groups (BPZE1, BPZE1 + Boostrix, BPZE1 and BPZE1 + Boostrix, Boostrix control). The likelihood ratio chi-square test will be used to compare the proportions between treatment groups.

Separate relative risks, which are defined as the ratio of two treatment group proportions, will be calculated for 1) BPZE1 vs. BPZE1 + Boostrix; 2) BPZE1 vs. Boostrix control; 3) BPZE1 + Boostrix vs. Boostrix control; 4) BPZE1 and BPZE1 + Boostrix vs. Boostrix control. The CI for relative risk will be computed using the likelihood ratio method.

The relative risk reduction (RRR) is defined as $RRR (\%) = (1 - RR) \times 100$. The CI for the RRR will be obtained by transforming the CI for the relative risk using $(1 - UL, 1 - LL)$, where UL denotes the upper limit of the CI for the RR and LL denotes the lower limit of the CI for the RR.

The hypotheses for the primary endpoint are:

H0: RRR $\leq 0\%$

HI: RRR $> 0\%$

Rejection of the null hypothesis demonstrates a statistically significant vaccine effect, (i.e., LL of the CI $> 0\%$), and will be considered to meet the pre-specified study success criterion.

Colonization at Day 8 safety lead-in group will be analyzed to determine specimen type. Colonization at Day 29 or Day 85 will be analyzed for clearance of BPZE1.

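### SAP 8.4.1 gives the substudy colonisation test a primary label and a study-success criterion that contradict the SAP's own success rule, and does not name the contrast tested

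*SAP*

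**What the plan says.** SAP 8.4.1 analyses colonisation at Day 92 or Day 99 after the Day 85 BPZE1 challenge. It begins its list of contrasts thus: "Separate relative risks, which are defined as the ratio of two treatment group proportions, will be calculated for 1) BPZE1 vs. BPZE1 + Boostrix". The other three are BPZE1 vs Boostrix, BPZE1 + Boostrix vs Boostrix, and the two BPZE1 groups pooled vs Boostrix. After defining RRR as (1 − RR) × 100, it continues "The hypotheses for the primary endpoint are", sets H0: RRR ≤ 0% against RRR > 0%, treats rejection as showing a significant vaccine effect, and adds that rejection "will be considered to meet the pre-specified study success criterion".

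Elsewhere the plan is consistent and different:

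- **Primary endpoint.** SAP 3.2.1 and the estimand table in SAP 8.1 name the Day 29 fold rise in mucosal S-IgA against whole cell extract, in the BPZE1 and BPZE1 + Boostrix groups.
- **Success rule.** SAP 8.1: "The study is considered a success if both primary comparisons meet statistical significance". Protocol 7.4 has the same rule.
- **Colonisation, secondary tier.** SAP 2.2.2: "To describe colonization in each of the groups: BPZE1, BPZE1 + Boostrix, BPZE1 and BPZE1 + Boostrix, Boostrix control". The matching endpoint in SAP 3.2.2.2 is a proportion.
- **Colonisation, exploratory tier.** SAP 2.3.3: "To demonstrate prior vaccination with BPZE1 substantially reduces colonization at Days 92 and Day 99". SAP 3.2.3.3 places the percentage reduction against control here.
- **Substudy population.** Opt-in and open-label, up to 120 subjects (SAP 3.1). Protocol 5.1 concedes: "It is recognized this may introduce some subject bias due to the opt-in nature".

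**The concern.** A plan can have only one definition of study success. Here the SAP has two: one in 8.1 on S-IgA and one in 8.4.1 on colonisation. Nothing resolves the conflict. The precedence clause in SAP Section 1 ranks the SAP above the protocol, but this contradiction lies inside the SAP, and the clause also stops the protocol from correcting 8.4.1. SAP Section 11, which lists changes to the planned analysis, mentions only the added 10 to 17 year age group.

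The test is also not specified well enough to carry a success claim. One hypothesis pair follows four relative risks, and the text does not say which it applies to. In the first contrast both groups received BPZE1, so a positive RRR would say something about adding Boostrix but could not show the vaccine effect that the text asserts.

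Taken as an alternative to 8.1, the wording offers a route to success for a study that misses its S-IgA objective. Taken as an extra requirement, it adds a hurdle of unknown power, and the stated 90% overall power no longer describes study success.

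**Working it through.** **1. The plan's own power figure (SAP 4.1.1).** Inputs: n = 108 per group, standardised effect 0.35, paired t-test, two-sided 0.05.

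- Noncentrality: 0.35 × √108 = 3.637, with 107 degrees of freedom.
- Power from the noncentral t distribution: 0.950 (normal approximation: 0.953).
- Both comparisons: 0.950² = 0.902.

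The stated 95% and 90% are reproduced. Because both comparisons must succeed at one-sided 0.025 (SAP 8.1), the chance of false success under that rule is at most 0.025. SAP 4.1.1 and 4.1.2 cover only S-IgA and serum IgG; no power is stated for colonisation.

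**2. What 8.4.1 would add if read literally.** SAP 8.4.1 gives no level for the confidence interval of the relative risk. I take 95%, in line with the two-sided 0.05 rule in SAP Section 4, so each contrast has a nominal one-sided error of 0.025.

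- Four independent contrasts: 1 − (1 − 0.025)⁴ = 0.096.
- Bonferroni sum: 4 × 0.025 = 0.100.

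The contrasts share arms, so I simulated them. With a likelihood-ratio interval, the lower limit of RRR exceeds 0 exactly when the first group's observed proportion is lower and the likelihood-ratio statistic exceeds 3.84. There were 400,000 trials per scenario, with the same true colonisation rate in all arms.

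Arm sizes and rates are my assumptions, because the documents give neither. With up to 120 subjects and equal uptake, 120 / 3 = 40 per arm is the largest equal split; I also used 20 and 30. Rates were 0.3, 0.5, 0.7 and 0.9. The table gives the range over the four rates.

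| Per arm | Pooled vs Boostrix only | Any of three vs Boostrix | Any of four |
|---|---|---|---|
| 20 | 2.7–4.6% | 4.4–7.2% | 6.1–10.7% |
| 30 | 2.4–4.1% | 4.9–6.1% | 7.0–9.4% |
| 40 | 2.5–3.6% | 5.1–5.5% | 7.3–8.3% |

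The highest values occur at a rate of 0.9. There the likelihood-ratio interval is itself somewhat liberal in small arms (4.6% for the single pooled contrast at 20 per arm), which is how the any-of-four figure can pass the nominal 10% sum.

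**3. After the correction.** With success defined only in SAP 8.1, the bound of 0.025 and the power of 0.950 per comparison and 0.902 overall stand unchanged.

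**The case against.** The best defence is that two stray phrases are being over-read. The true primary is fixed consistently in the endpoint list, the estimand, the sample size and the success rule. Declaring success on colonisation after failing S-IgA would contradict all of these. That is a fair account of the likely intent, but it does not remove the second success criterion from the text.

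Several stronger readings are tempting, and the defence is right to resist them:

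- **That colonisation was only ever to be described.** This is true of the secondary objective. The exploratory objective is to demonstrate a reduction, Protocol 7.4.4 plans a percentage reduction with a 95% interval against Boostrix, and the rationale (Protocol Synopsis and Section 1.2) speaks of demonstrating protection as a secondary objective. An RRR analysis was planned; primary status and a success criterion were not.
- **That four tests are each a route to success.** SAP 8.4.1 calculates four relative risks but states a single hypothesis. The contrast is unspecified, which is a different defect.
- **That missing power and multiplicity control are faults in themselves.** For a secondary or exploratory endpoint they are not. They matter only because of the primary label and the success wording.
- **That self-selection invalidates the between-arm comparison.** Subjects come from randomised arms, site staff stay blinded to the Day 1 assignment until study end (Protocol 5.5.1), and opt-in closes at Day 85. Protocol 5.1 discloses the opt-in bias. The opt-in design is a reason not to rest study success on this subset, but the documents do not show biased contrasts.

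**Conclusion.** The point stands as a wrong decision rule in SAP 8.4.1. A secondary and exploratory substudy analysis is called the primary endpoint and given a study-success criterion, contrary to SAP 3.2.1 and 8.1, and the tested contrast is not named.

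A reader might infer that the plan's false-success rate is 7 to 8%. The documents do not support that as a single figure. It belongs to one reading (any of four contrasts) at an assumed 40 per arm. Over the assumed range of 20 to 40 per arm and rates of 0.3 to 0.9, that reading gives about 6 to 11%. At 40 per arm, any of the three contrasts against Boostrix gives about 5%, and the pooled contrast alone 2.5 to 3.6%, not far from nominal. These figures describe the colonisation route by itself; a combined rate with the S-IgA rule was not computed. The contradiction does not depend on any of them.

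**What to change.** In SAP 8.4.1:

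1. Delete the reference to the primary endpoint and the sentence on the study-success criterion. State that study success is defined only in Section 8.1.
2. Label the RRR test non-confirmatory and exploratory, in line with SAP 2.3.3 and 3.2.3.3.
3. Tie the hypothesis to one named contrast against Boostrix control. The two BPZE1 groups pooled are a natural choice, since the objective in SAP 2.2.2 already lists them, but neither document ranks the contrasts and another contrast against Boostrix could be named.
4. Report the other relative risks with confidence intervals, descriptively. Attach no vaccine-effect hypothesis to BPZE1 vs BPZE1 + Boostrix.

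The cost is SAP wording only. Sample size, data collection, the primary test and its power do not change. The planned percentage reduction is still reported; the sponsor gives up only a primary and success status that the protocol does not give to colonisation. The change belongs before the interim database lock, by which SAP Section 1 requires the SAP to be final, because S-IgA results by treatment group may be released from that lock.

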8.4.2. Analysis of Mucosal Secretory Immunogenicity Endpoints

BPZE1, BPZE1 + Boostrix, BPZE1 and BPZE1 + Boostrix, and Boostrix control induction of mucosal S-IgA at Days 29 and 85 will be summarized by protection against colonization (Colonizers/Non-colonizers) and by treatment group and by timepoint. Separate two-sample t-tests will be used to compare the natural log-transformed GMRs at Days 29 and 85 between Colonizers and Non-colonizers by treatment group and by timepoint.

To test the hypothesis that BPZE1 and BPZE1 + Boostrix can induce mucosal S-IgA at Day 113 compared with Day 85, separate paired t-tests will be used to compare the natural log-transformed GMCs/GMRs at Day 113 with the natural log-transformed GMCs/GMRs at Day 85 within each treatment group. The corresponding 95% CIs will be calculated on the natural log scale, then both lower and upper limits will be exponentiated to get the 95% CIs on the original scale.

BPZE1, BPZE1 + Boostrix, or Boostrix control induction of mucosal S-IgA at Day 113 and Day 169/EOS will be summarized by participation in the substudy (Yes/No) and by treatment group and by timepoint. Separate ANCOVA models that include baseline S-IgA and an indicator of participation in the substudy (Yes/No) as covariates will be used to compare between subjects who participated in the substudy and subjects who did not participate in the substudy, by treatment group and by timepoint.

8.4.3. Analysis of Serum Immunogenicity Endpoints

To test the hypothesis that BPZE1 induction of serum immunity (IgA, IgG) at Day 113 compared with baseline, or Day 113 compared with Day 85, separate paired t-tests will be used to compare the natural log-transformed GMC at Day 113 with the natural log-transformed GMC at either baseline or Day 85 within each treatment group (BPZE1, BPZE1 + Boostrix, Boostrix). The corresponding 95% CIs will be calculated on the natural log scale, then both lower and upper limits will be exponentiated to get the 95% CIs on the original scale.

BPZE1, BPZE1 + Boostrix, and Boostrix induction of serum immunity (IgA, IgG) at Day 113 and Day 169/EOS will be summarized by participation in the substudy (Yes/No) and by treatment group and by timepoint. Separate two sample t-tests will be used to compare the natural log-transformed GMCs at Day 113 and Day 169/EOS between subjects who participated in the substudy and subjects who did not participate in the substudy (Day 169/EOS only), by treatment group and by timepoint.

BPZE1, BPZE1+Boostrix, BPZE1 and BPZE1+Boostrix, Boostrix control induction of serum immunity (IgA, IgG) at Days 29 and 85 will be summarized by protection against colonization (colonized/non-colonized) and by treatment group and by timepoint. Comparison between colonized subjects and non-colonized subjects will be made using separate two-sample t-tests by treatment group and by timepoint.

The number and proportion of subjects with $\geq 50\%$ killing titer (or equivalent) at Day 113 compared to baseline and Day 29 will be summarized by treatment group and by timepoint. The 95% CI will be provided by using Agresti-Coull method. A McNemar test will be used to compare proportions between timepoints in each treatment groups (Day 113 vs baseline; Day 113 vs Day 29).

The number and proportion of subjects with a $\geq 2x$ increase from baseline in SBA bactericidal titer (50% killing titer) will be summarized by treatment group, by timepoint and by strain. The 95% CIs for each treatment group will be computed using the Agresti-Coull method and the 95% CIs for the difference in proportions between groups (BPZE1 vs Boostrix, BPZE1 + Boostrix vs Boostrix) will be computed using Agresti Caffo method. A chi-square test will be performed to compare the proportion of subjects between groups (BPZE1 vs Boostrix, BPZE1 + Boostrix vs Boostrix) with a $\geq 2x$ increase in SBA bactericidal titer and two-sided p-value will be provided.

Reverse cumulative distribution curves will be provided for SBA (PRN+ and PRN-) at baseline, Day 29 and Day 113.

9. Safety Analysis

Unless otherwise specified, safety analysis will be performed based on the Safety Analysis Set. Safety analysis for safety lead-in cohort will be performed based on the Safety Lead-in Analysis Set. All summaries and analyses will be presented by treatment groups (BPZE1, BPZE1 + Boostrix, Boostrix), age group, and overall for first study vaccination and following re-vaccination/attenuated challenge (substudy) separately.

9.1.Solicited Adverse Events

The number and percentage of subjects with any solicited AEs (local, nasal/respiratory, and systemic reactogenicity events) through 7 days following first study vaccination with any

combination of pertussis-containing vaccines (BPZE1, BPZE1 + Boostrix, Boostrix) will be calculated by treatment group, age group and overall, and by timepoint.

Solicited reactogenicity events occurring from the time of study vaccination on Day 1 for 7 consecutive days starting the day following study vaccination, including local, nasal/respiratory reactions and systemic reactogenicity, will be summarized as presenting both the number and frequency, categorized by the severity grades according to respective reactogenicity grades (Table 9-1-1, Table 9-1-2, and Table 9-1-3).

Additionally, solicited AEs will be analyzed by determining the maximum severity through 7 days following study vaccination on Day 1 to summarize the frequency and percentage of subjects reporting each local, nasal/respiratory, or systemic event.

Redness measurements, swelling measurements, and oral temperature if subjects have fever for 7 days following vaccination will be summarized using descriptive statistics.

Duration through 7 days following study vaccination and duration through resolution following study vaccination will be summarized using descriptive statistics. Duration through 7 days is defined as days with the reactogenicity event onset through 7 days following vaccination per patient reported daily diary. Duration beyond 7 days is defined as days with the reactogenicity event continuing beyond 7 days as captured in adverse events.

Solicited AEs will be reported separately using the same methods above following study vaccination on Day 85 in the substudy.

Table 9-1-1 Local Reactogenicity Grading Scale

Variable	Grade 1	Grade 2	Grade 3
Pain/tenderness ^a	Easily tolerated, causes no or minimal limitation of use of limb	Sufficiently discomforting, interferes with greater than minimal limitation of use of limb	Causing inability to perform usual social and functional activities
Redness ^{b,c}	Evidence of redness that is ≤ 2.5 cm in diameter	>2.5 cm in diameter with $<50\%$ of upper extremity surface area segment involved	$\geq 50\%$ upper extremity surface area segment involved OR ulceration OR infection OR phlebitis OR sterile abscess OR drainage
Swelling ^{b,c}	Evidence of swelling that is ≤ 2.5 cm in diameter	>2.5 cm in diameter with $<50\%$ of upper extremity surface area segment involved	$\geq 50\%$ upper extremity surface area segment involved OR ulceration OR infection OR phlebitis OR sterile abscess OR drainage

Note: Local reactogenicity to be evaluated after an IM injection only. Grade 0 will be the classification if the observation is less than a grade 1. Any grade 3 reactogenicity event that leads to an unscheduled visit to a healthcare provider will be recorded as an MAAE.

^a To be graded by investigator based on subject diary.

^b Grade to be applied by data management based on measurement recording unless grade 3 is noted with other characteristics by the investigator.

- c If redness or swelling exceeds 100 mm or >50% of upper extremity surface area, or involves the shoulder, elbow, or chest, or prevents everyday activity, then subjects must be evaluated and a swelling assessment eCRF will be completed.

Source: Adapted from DAIDS Version 2.1, 2017.

Table 9-1-2 Nasal/Respiratory Reactogenicity Grading Scale

Variable	Grade 1	Grade 2	Grade 3
Runny nose/nasal congestion	Noticeable but does not interfere with normal everyday activity (eg, aware but not troubled, rarely wipes/blows nose, breathing through nose noted)	Moderate discomfort that interferes with normal everyday activity, troublesome (eg, wipe/blow nose occasionally, noisy nose breathing, occasional mouth breathing, “nasally” speech)	Significant discomfort, prevents normal everyday activity, and/or seeks medical care (eg, wipe/blow nose frequently, mouth breathing most of the time due to congestion, consistent “nasally” speech)
Sore/irritated throat (“scratchy”)	Noticeable but does not interfere with eating or drinking (eg, aware but not troubled)	Moderate discomfort that interferes with eating or drinking, troublesome, affects oral intake	Significant discomfort, prevents eating or drinking, and/or seeks medical care; troublesome to the level of preventing oral intake
Cough	Noticeable but does not interfere with normal everyday activity or sleeping (eg, aware but not troubled, a few short episodes)	Frequent cough that interrupts normal everyday activity or sleeping, troublesome (eg, coughing but only rare episodes of prolonged coughing)	Significant and repetitive coughing that prevents everyday activity or sleep, or seeks medical care (eg, frequent coughing, occasional episodes of prolonged coughing)
Sneezing	Noticeable but does not interfere with normal everyday activity (eg, aware but not troubled, a few short episodes)	Moderate discomfort that interferes with normal everyday activity, troublesome (eg, occasional bouts of sneezing)	Significant discomfort, prevents everyday activity, and/or seeks medical care (eg, frequent/repeated sneezing episodes)
Nasal or sinus pain/irritation	Noticeable but does not interfere with normal everyday activity (eg, aware but not troubled, noted discomfort)	Moderate discomfort that interferes with normal everyday activity, troublesome (facial pain/pressure)	Significant discomfort, prevents everyday activity, and/or seeks medical care; or induces nosebleed ^a
Difficulty breathing/wheezing	Audible wheeze (whistling sound) occasionally noted with exhale or inhale but does not interfere with normal everyday activity	Audible wheeze and or shortness of breath with activity (eg, nasal flaring, chest tightness, rapid breathing at rest/minimal activity), interferes with normal everyday activity	Requires bronchodilator use or accompanied by respiratory distress or hypoxemia

Note: Grade 0 will be the classification if the observation is less than a grade 1. Any grade 3 reactogenicity event that leads to an unscheduled visit to a healthcare provider will be recorded as an MAAE.

^a Epistaxis (nosebleed) should be entered as an AE and graded accordingly.

Source: Adapted for age and aligned with FluMist Monograph.

Table 9-1-3 **Systemic Reactogenicity Grading Scale**

Variable	Grade 1	Grade 2	Grade 3
Fever ^a	38.0 – 38.4 °C (100.4°F – 101.1°F)	38.5 – 38.9 °C (101.2°F – 102.0°F)	39.0 – 40.0 °C (102.1°F – 104.0°F)
Headache	Easily tolerated, causing no or minimal interference with daily activities	Causing greater than minimal interference with usual social and functional activities Interferes with normal everyday activity	Prevents performance of normal social and functional activities
Fatigue/malaise (decreased activity)	Easily tolerated	Interferes with normal everyday activity	Prevents normal everyday activity
Loss of appetite/anorexia	loss of appetite but no decrease in oral intake	Decreased oral intake but no weight loss	Decreased oral intake with weight loss or evidence of dehydration
Vomiting	Transient or intermittent AND no or minimal interference with oral intake	Frequent episodes with no or mild dehydration	Persistent vomiting resulting in need of aggressive rehydration (e.g. IV hydration)
Diarrhoea	Transient or intermittent episodes of unformed stools OR increase of ≤ 3 stools over normal in a 24-hr period	Persistent episodes of unformed or watery stools OR increase of 4-6 stools over normal in a 24-hr period	Increase of ≥ 7 stools a 24-hr period OR IV fluid replacement indicated
Nausea	Transient or intermittent AND no or minimal interference with oral intake	Persistent nausea with decrease in oral intake for 24 hrs	Persistent nausea with need for fluid replacement (eg, IV hydration)
Myalgia (muscle aches)	Muscle pain beyond the site of injection causing no or minimal interference with usual social and functional activities	Muscle pain beyond the site of injection causing greater than minimal interference with usual social and functional activities	Muscle pain causing inability to perform usual social and functional activities
Acute allergic reaction/urticaria	Localized without medical intervention	Localized with medical intervention OR mild angioedema without intervention	Generalized OR angioedema with intervention

Note: Grade 0 will be the classification if the observation is less than a Grade 1. Any grade 3 reactogenicity event that leads to an unscheduled visit to a healthcare provider will be recorded as an MAAE.

^a Temperature may be oral, tympanic, or noncontact (clinic only). Temperature greater than 40.0 °C (104.0 °F) is considered an SAE and subjects should seek medical attention immediately.

Source: Adapted from DAIDS Version 2.1, 2017.

9.2.Unsolicited Adverse Events

Unsolicited AEs will be coded according to Medical Dictionary for Regulatory Activities (MedDRA) latest version. Unless otherwise specified, unsolicited AEs will be summarized by System Organ Class (SOC), FDA Medical Query (FMQ) and Preferred Term (PT), with SOCs sorted in the alphabetical order and PTs within each SOC in descending order of subject incidence.

TEAE is defined as an AE that starts or an existing AE that worsens on or after the date of vaccination. AEs will be summarized by treatment groups, age group, and main study and substudy separately. In general AEs will be summarized from Day 1 to end of study for overall and subjects in substudy. AEs from Day 85 to end of study for subjects in substudy will be summarized separately. Between screening and Day 1, AEs will be collected if classified as SAEs or if considered related to study procedure or study involvement. All AEs regardless of causality will be recorded for 28 days after any vaccination/challenge and summarized. All AESI and SAE will be recorded and summarized from the time of vaccination to Day 169/EOS. All MAAEs occurring through 84 days following any vaccination (and through EOS) will be recorded and summarized.

